## DATA

We will obtain socio-demographic and clinical variables:

- Age (years)
- Sex
- Height (cm)
- Weight (kg)
- Level and side of amputation
- Duration of pain (weeks)
- Date of amputation
- Etiology of amputation
- Baseline NRS score for both PLP/RLP (worst, least, average, current)
- Site of residual limb maximal pain (measured by distance from posterior superior iliac spine (PSIS) to most painful point [in cm])
- Analgesic medication log: dose and frequency of each medication participant currently taking
- OPUS: Lower-Extremity Functional Status Measure Subsection Score
- GARS

## POWER ANALYSIS

Power and sample size calculations for this clinical trial were performed based on the data from a small cross-over study (N = 8) by Casale et al. The primary outcome variable will be achievability of  $\geq 50\%$  pain relief (dichotomous variable with yes/no), calculated from pre- and post-inject NRS in each of the lidocaine and sham conditions (i.e., pre-injection NRS – post-injection NRS). Based on the data from Casale et al., along with our expected, overall success rate of 75% by lidocaine injection, we calculated the difference in two proportions of discordant pairs to be 0.625 and the overall proportion of discordant pairs to be 0.875. Using these values and binomial enumeration (1,500 enumerations), along with an

STU#:

alpha level of 0.05, a power of 0.80, a two-sided t-test, and a dropout rate of 10%, the sample size was estimated as 20.

#### STATISTICAL PLAN

Data for the primary outcome variable, proportion of participants reporting  $\geq 50\%$  immediate pain reduction from baseline, will be reported as the mean and standard deviation (or median and interquartile range if not normally distributed) of the lidocaine and sham groups. Mean change in pain score, will be examined using an unpaired t test (NCSS) (or Mann-Whitney U test if not normally distributed). The median difference and its 95% CI will be calculated. The criterion for rejection of the null hypothesis will be  $P < 0.05$ .

Participant data and secondary variables that are characterized by nominal data will be summarized as the number of participants in each category and the percentage of all participants in the group that they represent. These variables will be compared between the groups using the Pearson  $\chi^2$  test, or when at least one of the cells of the contingency table had an expected number less than five, the Fischer exact probability test. The Miettinen-Nurminen score will be used to calculate 95% CIs for differences in percentages where indicated.

Variables that are characterized by ordinal data and non-normally distributed continuous data (e.g., procedure time) will be summarized as median and interquartile range. These variables will be compared between the groups using the Mann-Whitney U test. Median differences and their 95% CIs will be calculated where indicated.

Variables that are characterized by normally distributed continuous data (e.g., age and body weight) will be summarized as mean and standard deviation. These variables will be compared between the groups using the unpaired t test (NCSS). Mean differences and their 95% CIs will be determined.

In case there were significant differences in the demographic variables, multivariate logistic and linear regression analyzes will be conducted to examine the binary and continuous outcome variables by group, while accounting for the statistically significant demographic variables analysis will be used to determine if any demographic or clinical variables (age, BMI, duration of pain, etc.) are independently associated with successful pain (NRS) outcomes.

Lastly, Pearson's correlation coefficients will be computed to assess the relationships among various demographic and procedural covariates.

STU#:

STU#:

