## **STUDY ENDPOINTS:**

### Primary Outcome

Comparison of the proportions of participants reporting  $\geq 50\%$  improvement in NRS pain score from baseline at 15 minutes in treatment and sham groups

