### *Visit 2 (procedure 1)– Randomization and Study Intervention*

STU#:

Eligible participants will return to the Lavin 14th floor Pain clinic within 2 weeks of the initial visit. Participants will be randomized to treatment or sham group. Participant pre-procedure 1 NRS pain score will be collected. Individual pain log will start 15 minutes after procedure. Participant will log pain score every hour until asleep. The next day, participant will record daily NRS pain score for 5 days.

Randomization

A computer-generated 1:1 block randomization scheme (<https://www.randomizer.org>) will be used to assign participants to receive a peri-sciatic nerve injection with either 10 mL of 2% lidocaine or 10 mL of preservative-free saline (compounded by the 11th floor Lavin pharmacy and labeled with a “1” or “2” to ensure adequate blinding). Randomization will be performed by a research assistant by opening an opaque envelope to reveal the participant number and group assignment printed inside of the envelope. This will instruct authorized study personnel to draw up either 2% lidocaine or saline (labeled “1” or “2” by compounding pharmacy per above). The blinded injectionist will be provided an unlabeled syringe of injectate immediately before the injection procedure. Participants, injectionist, and study personnel who collect outcomes data will be blinded to group assignment.

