Treatment block of sciatic nerve in contralateral limb: Procedure planning will be based on the participant’s indication of residual limb point of maximal pain (measured by distance from posterior superior iliac spine (PSIS) to most painful point [in cm]). Note that this point may beyond the anatomic end of the residual limb. The block will be performed at the exact same distance from PSIS on the contralateral side. If the block cannot be performed at this site due to anatomic or technical considerations (such as proximity to vascular structures), a more cephalad site along the sciatic nerve course will be selected for the procedure. During the block procedure, the participant will be positioned prone. Standard American Society of Anesthesiologists (ASA) procedure monitoring will be used (pulse oximetry, ECG, blood pressure, and heart rate). The participant’s skin will be prepared with chlorhexidine. A sterile ultrasound probe will be placed on the participants’ residual limb at a transverse angle in order to view the nerve in short-axis. The skin will be anesthetized with 1-2 mL of 1.0% lidocaine. The ultrasound probe (in plane) will be advanced to the intact limb’s sciatic nerve equidistance to that of the residual limb point of maximal pain. A 22-gauge standard echogenic needle will be placed adjacent to the sciatic nerve with ultrasound guidance. At the site of the nerve, 10mL of 2% lidocaine will be injected through the needle in the intervention group and 10ml of saline will be injected in the sham group.

In treatment group: At the site of the nerve, 10mL of 2% lidocaine will be injected through the needle

In control group: At the site of the nerve, 10ml of saline will be injected through the needle

Following injection, participants will be kept in recovery area and monitored for 30 minutes. They will also complete a pain log starting 15 minutes post-injection. After the first pain score is recorded, the participants will dress and exit procedure area. Participants will be required to arrange transportation as the block may impair lower extremity motor function.

Both saline and local anesthetic will be administered to all subjects with a crossover design as described above. Participants will undergo 5-day washout between injections.

*Visit 3 – Crossover for both groups*

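### The primary endpoint is a paired yes/no responder outcome, but the only test in the primary-analysis paragraph is an unpaired t test on mean pain change

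*Combined protocol and SAP*

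**What the plan says.** Three sections of the combined protocol and SAP bear on the primary comparison.

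- **Endpoint.** The Primary Outcome section specifies "Comparison of the proportions of participants reporting" at least 50% "improvement in NRS pain score from baseline at 15 minutes in treatment and sham groups". The hypothesis under OBJECTIVES uses the same proportion. The POWER ANALYSIS describes the variable as "pain relief (dichotomous variable with yes/no), calculated from pre- and post-inject NRS in each of the lidocaine and sham conditions".
- **Design.** The Visit 2 section states: "Both saline and local anesthetic will be administered to all subjects with a crossover design as described above". Randomization is therefore to the order of the two injections, and each participant contributes one result under each condition.
- **Sample size.** The POWER ANALYSIS says "we calculated the difference in two proportions of discordant pairs to be 0.625 and the overall proportion of discordant pairs to be 0.875". It uses binomial enumeration, alpha 0.05, power 0.80 and 10% dropout to reach 20, but labels the test a two-sided t-test.
- **Analysis.** The first paragraph of the STATISTICAL PLAN names the responder proportion as primary, then says it "will be reported as the mean and standard deviation (or median and interquartile range if not normally distributed) of the lidocaine and sham groups". The next sentence gives the only test in the paragraph: "Mean change in pain score, will be examined using an unpaired t test (NCSS) (or Mann-Whitney U test if not normally distributed". A median difference with 95% CI follows, and then the P < 0.05 rejection criterion.

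Elsewhere in the STATISTICAL PLAN, Pearson chi-square or Fisher tests with Miettinen-Nurminen intervals are assigned to participant data and secondary nominal variables. Logistic regression is planned only if demographic variables differ significantly.

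**The concern.** The primary paragraph departs from the endpoint and the design in two ways. It tests mean NRS change instead of the responder proportion, and it uses an independent-samples test although the same people supply both columns. Mean and SD, or median and IQR, are also not useful summaries of a yes/no variable.

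Read literally, the trial could reject its null on a shift in mean pain without showing any difference in responders, and the stated 80% power would describe a test that is never run. With about 18 completers, the choice among a t test, Mann-Whitney, chi-square and McNemar can decide the conclusion. The present text leaves that choice open until the data are in hand.

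**Working it through.** **1. Reproduce N = 20.** Inputs from the POWER ANALYSIS: total discordant proportion 0.875, difference 0.625, two-sided alpha 0.05, power 0.80, dropout 10%.

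- Lidocaine-only responders: p10 = (0.875 + 0.625)/2 = 0.750.
- Sham-only responders: p01 = (0.875 − 0.625)/2 = 0.125.
- Exact McNemar: the discordant count m is Binomial(n, 0.875). Given m, the number favouring lidocaine is Binomial(m, 0.750/0.875). Reject when the two-sided exact binomial p is at most 0.05.

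| Pairs | Power |
|---|---|
| 17 | 0.790 |
| 18 | 0.830 |
| 20 | 0.879 |

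Eighteen pairs are needed, and 18/(1 − 0.10) = 20, which matches the plan. The asymptotic McNemar formula gives 15 pairs (17 after dropout), or 17 pairs (19 after dropout) with continuity correction. The exact paired binary test, which fits the binomial enumeration named in the plan, is the version that returns 20.

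**2. Search for a test that fits a paired binary outcome.**

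| Method in the STATISTICAL PLAN | Assigned to | Binary? | Paired? |
|---|---|---|---|
| Unpaired t / Mann-Whitney | Mean change in pain score | No | No |
| Pearson chi-square / Fisher, Miettinen-Nurminen CI | Participant data and secondary nominal variables | Yes | No |
| Logistic regression | Only if demographics differ | Yes | No within-person term |

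McNemar, a paired binomial test, conditional logistic regression and mixed models are all absent. The general linear model for crossover sequence in the Secondary Outcomes list concerns secondary analyses only.

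**3. What the wrong variable can do (illustration; all inputs assumed).** Take n = 18, baseline NRS 7, mean change 2.0 on lidocaine and 0.5 on sham, SD 1.5, within-person correlation 0.3, normal changes.

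- A responder needs a fall of at least 3.5. Lidocaine: (3.5 − 2.0)/1.5 = 1 SD above the mean, about 16%. Sham: (3.5 − 0.5)/1.5 = 2 SD, about 2%.
- By simulation, the unpaired t test rejects 87% of the time and exact McNemar on responders rejects 3%.

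**4. What ignoring the pairing does if chi-square/Fisher is used for the responder outcome.** The plan expects 75% success on lidocaine. That equals p10, so the proportion responding to both is 0.75 − 0.75 = 0 and the sham rate is 0.125.

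- Implied correlation: (0 − 0.75 × 0.125)/√(0.75 × 0.25 × 0.125 × 0.875) = −0.655.
- Paired SE of the difference at n = 18: √((0.875 − 0.625²)/18) = 0.164.
- SE treating the columns as independent: √((0.75 × 0.25 + 0.125 × 0.875)/18) = √((0.1875 + 0.1094)/18) = 0.128, which is 22% smaller.

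Type I error of the chi-square/Fisher rule at n = 18 was found by multinomial enumeration. The common true response rate is assumed to be 0.4375, the average of 0.75 and 0.125:

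| Within-person correlation | Rejection rate under the null |
|---|---|
| −0.655 | 15.1% |
| 0 | 6.3% |
| +0.2 | 3.7% |
| +0.3 | 2.6% |
| +0.5 | 0.9% |

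**The case against.** The strongest defence is that the t-test sentence is misplaced secondary text. Mean NRS change is listed as a secondary outcome from 1 hour onward, and the P < 0.05 line can be read as a general alpha. That reading is possible, but it leaves the primary proportion with no test at all. Stretching the nominal-data sentence to cover the primary goes beyond its wording and is still unpaired.

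Several limits on the numbers do stand.

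- A t-test sample size cannot be excluded, because the documents give no SD for NRS change. The supportable statement is that N = 20 follows from the stated inputs as exact McNemar.
- The 15.1% rests on a correlation implied by planning inputs drawn partly from an 8-person study. Some of the excess over 5% is small-sample chi-square error, since the rule already gives 6.3% at zero correlation. With positive correlation the rule is conservative, so the direction of error is unknown.
- The 22% figure compares simple large-sample SEs, not the Miettinen-Nurminen intervals the plan names.
- The 87% versus 3% illustration uses a real 1.5-point difference and a lidocaine responder rate far below the planned 75%. It shows that the two tests answer different questions; it does not estimate a false-positive rate.
- If the planned effect is real, the chi-square/Fisher rule at 18 pairs would reject about 97% of the time, so the headline result might well be the same.

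None of this supplies a valid test for the primary hypothesis.

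**Conclusion.** The concern holds. The analysis plan differs from the endpoint, the design and the sample-size basis both in the variable tested and in its treatment of pairing, and no alternative reading gives the paired binary primary outcome a valid test. This should be corrected before analysis because it concerns the confirmatory test of the only primary hypothesis.

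The firm number is the reproduction of N = 20 as an exact McNemar design with 83.0% power at 18 completers, using only the plan's inputs. The size of the error from an unpaired test is not firm: it runs from 0.9% to 15.1% over the correlations shown, under an assumed common rate of 43.75%, and the documents give no correlation with which to narrow it. The sample size itself is not at fault.

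**What to change.** Rewrite the first paragraph of the STATISTICAL PLAN so that:

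1. The primary analysis compares responder status (at least 50% fall from that period's pre-injection NRS to 15 minutes, in line with the per-condition calculation in the POWER ANALYSIS) between lidocaine and sham within participant, by exact McNemar test at two-sided 0.05.
2. Results are reported as n/N and percent per condition, with the paired difference in proportions and a paired 95% CI, for example Newcombe or Tango.
3. The P < 0.05 criterion for the primary hypothesis applies to this test only.
4. Mean NRS change is labelled secondary.

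In the POWER ANALYSIS, replace the t-test label with exact McNemar test. A period-adjusted companion analysis (Mainland-Gart, or conditional logistic regression with period) is a sensible addition, though not needed to cure the defect.

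The cost is protocol and SAP wording. N stays at 20, and no new data, participants or visits are required.

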### Secondary Outcomes (between and within-group comparisons will be used for each outcome):

- 1) Mean and standard deviation (SD) of change in NRS pain score at 1, 2, 3, 4, 5, 6, 24, 48, 72, 96, 120 hours post-saline and lidocaine injections
- 2) Mean and SD of average daily steps recorded at 24, 48, 72, 96, 120 hours post-saline and lidocaine injections (via Modus StepWatchTM or Evolution EvoWalkTM)

STU#:

- 3) Mean and SD of change in Orthotics and Prosthetics User's Survey (OPUS) score immediately post-injection and conclusion of washout (5 days) in saline and lidocaine groups
- 4) Mean and SD of change in Groningen Activity Restriction Scale (GARS) score immediately post-injection and conclusion of washout (5 days) in saline and lidocaine groups
- 5) General linear model analysis of the interaction between crossover sequence
- 6) Demographic factors associated with large improvement in NRS pain score
- 7) Complications associated with the procedures

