Eligible participants will return to the Lavin 14th floor Pain clinic within 5 days of visit 2. Participant pre-procedure 2 NRS and OPUS will be collected. Note that this will serve as post-procedure 1 washout and pre-procedure 2 intervention data point.

Both groups: will cross over and undergo treatment as described in *Visit 2*. Participant pain log will start 15 minutes after procedure 2. Participant will log pain scores every hour until asleep. The next day, participant will record daily NRS pain score for 5 days.

*Telephone call 1,2,3:* participant will be called at 1- and 5-days post-procedures for NRS, OPUS survey and safety monitoring by research coordinator (see Safety Monitoring below).

**SAFETY MONITORING** Participants will be contacted one day following both interventions to assess for any adverse events or side effects.

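### Secondary lidocaine-versus-saline comparisons are assigned independent-samples tests and intervals although every participant receives both injections

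*Combined protocol and SAP*

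**What the plan says.** Under Visit 2 the protocol states: "Both saline and local anesthetic will be administered to all subjects with a crossover design as described above". The Power Analysis is paired as well: "we calculated the difference in two proportions of discordant pairs to be 0.625 and the overall proportion of discordant pairs to be 0.875".

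The Statistical Plan then names these methods for comparing groups:

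- Change in pain score: "Mean change in pain score, will be examined using an unpaired t test (NCSS) (or Mann-Whitney U test if not normally distributed".
- Normally distributed continuous variables: "These variables will be compared between the groups using the unpaired t test (NCSS). Mean differences and their 95% CIs will be determined".
- Ordinal and non-normal variables: Mann-Whitney U.
- Nominal participant data and nominal secondary variables: Pearson chi-square or Fisher's exact test. For intervals, "The Miettinen-Nurminen score will be used to calculate 95% CIs for differences in percentages where indicated".

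It names no paired t test, signed-rank test, McNemar test or mixed model. It also calls for regression adjustment if demographic variables differ significantly.

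The Secondary Outcomes list says that "between and within-group comparisons will be used for each outcome", without naming a test. Its item 5 reads "General linear model analysis of the interaction between crossover sequence", an interaction with only one factor stated.

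**The concern.** Each participant contributes a lidocaine value and a saline value for NRS change, steps, OPUS and GARS (secondary outcomes 1 to 4), and for any yes/no outcome such as complications. An independent-samples test treats 18 participants measured twice as 36 separate people. It ignores the covariance between the two values, so its standard error and interval are wrong unless that covariance is zero. Under positive correlation a crossover of 20 people gives up the precision that justified the design.

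The demographic rule does not fit the design either. The lidocaine and saline data sets consist of the same people, so with complete data their demographics cannot differ. Any difference between the two randomised sequences is chance.

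**Working it through.** **1. Is the planned N a paired calculation?** Inputs from the Power Analysis: discordant proportion 0.875, difference 0.625, two-sided alpha 0.05, power 0.80, dropout 10%.

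- Discordant in favour of lidocaine: (0.875 + 0.625)/2 = 0.75.
- Discordant in favour of saline: (0.875 − 0.625)/2 = 0.125.
- Exact McNemar power by binomial enumeration: 0.790 at 17 pairs and 0.830 at 18 pairs, so 18 pairs are needed.
- With dropout: 18/0.9 = 20, the stated N.

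The sample size therefore reproduces as a paired analysis, while the Statistical Plan lists unpaired ones.

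**2. Effect on the confidence interval.** Take n = 18 complete pairs, common SD σ and within-person correlation ρ. The documents give neither σ nor ρ for any secondary outcome, so ρ is assumed and differences are in SD units.

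- Unpaired half-width: t(34) × σ√(2/n), with t(34) = 2.032.
- Paired half-width: t(17) × σ√(2(1−ρ)/n), with t(17) = 2.110.
- Ratio, unpaired to paired: (2.032/2.110)/√(1−ρ) = 0.963/√(1−ρ).

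For example, at ρ = 0.5 the ratio is 0.963/0.707 = 1.36.

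**3. Effect on error rate and power.** Simulation of bivariate normal pairs, 200,000 replicates, n = 18, nominal two-sided 5%, power at an assumed true difference of 0.7 SD:

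| ρ (assumed) | CI ratio, unpaired/paired | Type I error, unpaired | Power, unpaired | Power, paired |
|---|---|---|---|---|
| 0 | 0.96 | 0.050 | 0.53 | 0.51 |
| 0.3 | 1.15 | 0.021 | 0.54 | 0.66 |
| 0.5 | 1.36 | 0.008 | 0.55 | 0.80 |
| 0.7 | 1.76 | 0.001 | 0.56 | 0.95 |

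The paired test holds about 0.050 throughout.

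**4. Sensitivity to the assumptions.**

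- Weak correlation: at ρ = 0.1 and 0.2 the CI ratio is 1.02 and 1.08, and power at 0.7 SD is 0.53 against 0.55 and 0.54 against 0.60 (unpaired against paired).
- Effect size: at ρ = 0.5, power is 0.25 against 0.52 for 0.5 SD, and 0.90 against 0.98 for 1.0 SD.
- Negative correlation: the unpaired test becomes anti-conservative, with type I error about 0.08 at ρ = −0.3 and 0.13 at ρ = −0.65.

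**The case against.** - **The quoted sentence sits in the primary-outcome paragraph, and the generic paragraphs use age, body weight and procedure time as examples.** Elsewhere the protocol uses groups to mean the randomised sequences, for which unpaired comparison of demographics is legitimate. This stands in part. The mismatch is explicit for change in pain score, which is secondary outcome 1, and for nominal secondary variables. For steps, OPUS and GARS it follows because the generic paragraphs are the only methods offered.
- **An unpaired t test of period differences between the two sequences is a valid crossover analysis.** That is true, but the plan does not describe it. It refers to lidocaine and sham groups.
- **The Secondary Outcomes list already promises within-group comparisons and a general linear model.** These show some intent. However, no paired lidocaine-minus-saline test is named, and the model is a separate, incomplete item.
- **The direction of the error depends on an unknown correlation.** This stands. If the 75% in the Power Analysis is the overall lidocaine response rate, then 0.75 of participants respond to lidocaine only. None are left to respond to both, and phi = (0 − 0.75 × 0.125)/√(0.75 × 0.25 × 0.125 × 0.875) = −0.65. That concerns the binary primary endpoint, but negative correlation cannot be excluded for the related NRS change. It would make the unpaired test liberal instead of conservative, which is a further reason to pair.
- **The loss may be small for change scores, and McNemar adds little for rare complications.** Both are fair. Outcomes 1, 3 and 4 are change scores and may be less correlated than steps, which are raw levels.
- **Eighteen complete pairs may not be available at every time point.** Hourly NRS is logged only until sleep, so later hourly pairs may be missing. The figures above are for complete pairs.

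**Conclusion.** The concern holds. The Statistical Plan assigns independent-samples tests and intervals to paired data, and it conflicts with the plan's own paired sample-size calculation. At an assumed correlation of 0.3 to 0.7 with 18 complete pairs, intervals are 15% to 76% too wide, and 12 to 39 percentage points of power are lost for a 0.7 SD difference. At zero correlation there is no loss. At zero or positive correlation the error does not create false positives. These sizes rest on assumed correlations, an assumed effect and normal data; that the method does not match the design needs no such assumption. It should be fixed before analysis. It is not more serious than that, because it concerns secondary outcomes and the likely error is conservative.

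**What to change.** - **Continuous and ordinal outcomes.** At each time point, analyse the within-participant lidocaine-minus-saline difference with a paired t test or Wilcoxon signed-rank test and a paired 95% CI. Alternatively, fit a crossover model per time point with fixed effects for treatment, period and sequence and a participant effect.
- **Yes/no outcomes.** Use McNemar's test with a confidence interval for paired proportions.
- **Joint modelling of time points, if chosen.** Include a participant-by-period random effect or an equivalent within-period covariance. A participant intercept alone is not enough. In a simulation with 11 NRS times per period, participant variance 0.4 of the total and participant-by-period variance 0.1 to 0.3 (all variances assumed), it gave type I error of 25% to 49% for the time-averaged effect. This is a caution about the remedy; the plan does not propose such a model.
- **Baseline adjustment.** Use the period's pre-injection value only where it is collected. Visit 3 states "Participant pre-procedure 2 NRS and OPUS will be collected" and does not list GARS.
- **Secondary outcome 5.** Complete it as a crossover model with treatment, period and sequence. Report the sequence term descriptively, as a low-powered and not clean check on carry-over.
- **Demographics.** Delete the adjustment triggered by significance and summarise demographics descriptively by sequence. Keep the predictor analysis that serves secondary outcome 6, which shares the same sentence.

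The cost is SAP wording and slightly more analysis programming. The paired tests need no data beyond those already listed for the secondary outcomes. Baseline adjustment of GARS would first need confirmation that it is collected before procedure 2.

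### The trigger for covariate adjustment cannot work in this crossover, the regressions ignore pairing, and the logistic predictor search has too few lidocaine non-responders to be reliable

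*Combined protocol and SAP*

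**What the plan says.** The Statistical Plan summarises the primary outcome by condition, "of the lidocaine and sham groups", and compares participant variables between groups with independent-samples tests (unpaired t, Mann-Whitney, chi-squared or Fisher). It then says: "In case there were significant differences in the demographic variables, multivariate logistic and linear regression analyzes will be conducted". Those regressions are by group and adjust for whichever demographic variables proved significant. The same run-on sentence goes on to look for variables that "are independently associated with successful pain (NRS) outcomes", naming age, BMI and duration of pain and leaving the list open. The Secondary Outcomes section makes this a stated outcome (item 6): "Demographic factors associated with large improvement in NRS pain score".

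On design, the Visit 2 section says "Both saline and local anesthetic will be administered to all subjects with a crossover design as described above". The same section also says "Participants will be randomized to treatment or sham group", so a reader could take the groups to be the two first-period assignments, that is, the two sequences. The plan does not say which is meant. The Power Analysis assumes an "expected, overall success rate of 75% by lidocaine injection", and "the sample size was estimated as 20".

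**The concern.** A demographic variable has one value per participant. If everyone contributes to both conditions, its distribution is the same under lidocaine and sham, so the test that decides on adjustment carries no information. If the groups are the sequences, randomisation makes any difference a chance event, and covariate choice becomes data-driven. Meanwhile the two quantities that do change between injections are not pre-specified: the pre-injection NRS, collected before each procedure, and the period. The regressions also contain no stated term linking a participant's two records.

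The predictor search raises a different problem. If most people respond to lidocaine, few non-responders remain to separate one candidate predictor from another. At stake are a secondary outcome reporting predictors that are artefacts of sparse data, and adjusted analyses that either never happen or leave out the useful covariates.

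**Working it through.** **Inputs.** From the Power Analysis: 20 participants, 10% dropout, 75% lidocaine success, discordant difference 0.625, discordant total 0.875, two-sided alpha 0.05, power 0.80. From the Statistical Plan: three named covariates, list open. From the Data section: 13 listed items, not all demographic.

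**The plan's own figure.** The two discordant proportions are (0.875 + 0.625)/2 = 0.75 and (0.875 − 0.625)/2 = 0.125. Exact two-sided McNemar power is 0.790 at 17 pairs and 0.830 at 18, so 18 pairs are needed, and 18/0.9 = 20. The sample size reproduces, and it rests on a paired comparison.

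**Trigger, groups read as lidocaine and sham.** Comparing 20 values with the same 20 values gives p = 1.0. Comparing 20 people with a random 18 of them, to mimic dropout, crossed 0.05 in 0 of 20,000 simulations.

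**Trigger, groups read as sequences.** The chance that at least one of k independent tests is significant is 1 − 0.95^k:
- k = 5: 23%
- k = 10: 40%
- k = 13: 49%

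These are approximate upper bounds: several listed variables are related (height, weight and BMI, for example), and exact tests are conservative at this size.

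**Lidocaine-only logistic model.** Expected non-responders are 20 × 0.25 = 5.0 (binomial 95% range 2 to 9), or 18 × 0.25 = 4.5 (1 to 8). For three covariates that is 5/3 = 1.7 non-responders per covariate. I simulated null, independent covariates and checked separation (no finite maximum-likelihood estimate) by linear programming:

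| Covariates | n = 20 | n = 18 |
|---|---|---|
| 3 continuous | 4% | 7% |
| 5 continuous | 17% | 24% |
| 3 continuous + 2 binary | 29% | 38% |

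Binary covariates were taken as evenly split; uneven ones separate more often. The shares move by a point or two between runs. Likelihood-ratio type I error for a single null covariate was about 10% with three covariates and 17% with five at n = 20 (11% and 19% at n = 18), against a nominal 5%.

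**Logistic model using both conditions.** With 75% success on lidocaine and a lidocaine-only response in 0.75 of pairs, nobody responds to both, and sham success is 12.5%. Expected responders are 20 × (0.75 + 0.125) = 17.5 of 40 records, or 18 × 0.875 = 15.75 of 36. The smaller class is therefore about 16 to 18, and sparsity is not the main fault; ignored pairing is. For a person-level covariate, treating two records as independent gives an approximate type I error of 2 × [1 − Φ(1.96/√(1 + ρ))], where ρ is the within-person correlation. The planning figures imply ρ = (0 − 0.75 × 0.125)/√(0.75 × 0.25 × 0.125 × 0.875) = −0.65.
- ρ = −0.65: about 0.1%
- ρ = 0: 5%
- ρ = +0.5: 11%

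The last value of ρ is an assumption; the documents give no observed correlation.

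**The case against.** The strongest reply is that little here touches the main result. If the trigger never fires, there is no adjusted result to call invalid. If it does fire, a person-level covariate is balanced across both conditions among completers, so in a linear model it leaves the treatment estimate unchanged. That stands. A reader might infer that the plan's adjusted results are invalid; the documents support only that the adjustment is almost never triggered, or is triggered by chance.

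A reader might also infer that every planned regression rests on about five non-responders. It does not. The count applies only to a logistic model of response after lidocaine, which the plan does not spell out. Linear models do not depend on it, and a logistic model on both conditions has a smaller class of about 16 to 18.

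A third tempting inference is that ignoring pairing inflates false positives to about 11%. That needs a correlation of +0.5, which no document supplies; the planning figures point the other way. The plan also never says that records will be stacked. It simply states no within-person term.

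It is fair to add that secondary outcome 5 plans a general linear model concerning crossover sequence, that the Power Analysis computes the endpoint from pre- and post-injection NRS, and that baseline NRS could enter through the open list. But the Statistical Plan does not link that model to these regressions, and computing change from baseline does not make baseline a pre-specified covariate. With only the three named covariates, separation is uncommon; the open list is what allows the worse figures.

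**Conclusion.** The concern holds in a limited form. The significance trigger has no workable reading in this design. The regressions lack a stated within-person term and omit pre-specified pre-injection NRS and period. Pairing error in a both-conditions model could make tests too liberal or too conservative. A multivariable logistic search on the lidocaine response would be unreliable, moderately so with three covariates and seriously so with five, and cannot carry a claim of independent association.

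This rests on the 75% success rate applying at 15 minutes, on 18 to 20 analysed participants, and on independent simulated covariates. It concerns adjusted and secondary analyses only. The sample size of 20 does not depend on it, so the change is advisable rather than essential to the primary question.

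**What to change.** - State whether groups means conditions or sequences. Delete the significance trigger and the baseline significance tests, and describe participant characteristics without p-values.
- Pre-specify pre-injection NRS and period as covariates in a model with treatment and a participant effect, and tie it to the general linear model in secondary outcome 5.
- For secondary outcome 6, use one row per person (response after lidocaine). Either limit the model to one or two covariates named in advance or use a penalised (Firth) logistic model. Report estimates with confidence intervals as hypothesis-generating, and drop the claim of independent association. Continuous NRS change after lidocaine may be added as a supporting analysis.

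The cost is analysis-plan text, including some rewording of the secondary analysis; visits, data collection and sample size do not change. What is given up is a multivariable predictor claim, which about five non-responders could not support.
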